3.2 Rationale and risk/benefit assessment

3.2.1 Rationale for study design, doses and control groups

The design of this study is standard for determining pharmacokinetics of a single dose of rosuvastatin calcium, atorvastatin calcium, and simvastatin.

The 20 mg rosuvastatin calcium, 40 mg atorvastatin calcium, and 40 mg simvastatin are clinically relevant doses, which are sufficient to allow complete characterization of their plasma concentration-time profiles.

The 3 way-crossover design is chosen to strengthen internal validity. The volunteers will serve as their own control for pharmacokinetic plasma profiles on all three study drugs.

3.2.2 Risk/benefit and ethical assessment

Rosuvastatin, atorvastatin, and simvastatin are marketed drugs and in general, are safe and well-tolerated when used according to prescribing information. While there is always a risk in taking any type of pharmaceutical product, the risk to healthy normal volunteers participating in this study is minimal.

There is no health benefit for healthy normal volunteers.

3.3 Selection of study population

3.3.1 Study selection record

Investigator(s) must keep a record of volunteers who were considered for enrollment but never enrolled e.g., subject screening log, according to local procedures. This information is necessary to establish that the volunteer population was selected without bias.

3.3.2 Inclusion criteria

For inclusion in the study volunteers must fulfill all of the following criteria:

1. Provision of signed written informed consent, ability to communicate with the investigator, and to understand and comply with the requirements of the study
2. Males and females aged 18-65, inclusive
3. Body Mass Index (BMI) 18-29 inclusive. BMI will be calculated as weight in kilogram (kg)/height in meters² (m²).
4. Women who are surgically sterilized, post-menopausal for at least one year, or not pregnant and/or lactating. Women of childbearing potential must be willing to abstain from sexual activity or use an effective double barrier method of contraception during the study period (e.g., condom and diaphragm, condom and foam, condom and sponge, etc.), or intrauterine devices

5. Chinese and Japanese volunteers must have parents of the same reported race. (See Section 4.1.1.1)
6. Residence in the United States for at least 12 months.

For inclusion in the genetic component of the study, volunteers must fulfill the following criterion:

1. Provision of signed written informed consent for genetic research

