3.3.3 Exclusion criteria

Any of the following is regarded as a criterion for exclusion from the study:

1. Use of prescription medication for a chronic medical condition
2. Acute illness or use of prescription medication for an acute medical condition within 2 weeks of Day -1A
3. History within the last 3 months of extreme or therapeutic diet programs including but not limited to: weight reduction, weight augmentation, high protein, high carbohydrate, low carbohydrate, or low fat
4. Any contraindication determined by review of a detailed medical and drug history, complete physical examination, vital signs, blood chemistry, hematology, and electrocardiogram (ECG).
5. Medical history or psychological conditions which, in the opinion of the investigator, would compromise the volunteer's safety or successful participation in the study
6. History of severe allergies
7. History of adverse drug reaction or hypersensitivity to statins or drugs with a similar chemical structure.
8. History or presence of gastrointestinal, hepatic, or renal disease or other conditions known to interfere with the ADME of drugs
9. History of alcohol or substance abuse within the past year
10. Positive test results for human immunodeficiency virus (HIV) antibody, hepatitis B surface antigen (HBsAG), or hepatitis C antibody
11. Positive urine drug screen
12. Participation in another study within 30 days of Day -1A, apart from non-invasive methodology studies in which no drugs were given.

13. Involvement in the planning and conduct of the study (applies to both AstraZeneca staff or staff at the study site)
14. Blood donation within 3 months of Day -1A.

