4.1 Medical examination and demographic measurements

4.1.1 Enrollment medical examination and demographic measurements

Each volunteer will undergo an enrollment medical examination and screening in the 35 days prior to Day -1A (screening period). This will consist of:

- Recording of demographic data - date of birth, sex, race (See Section [4.1.1.1](#))
- A standard medical history and a physical examination including the cardiovascular and respiratory systems
- A blood sample for standard clinical chemistry and hematology assessments a mid-stream urine sample for urinalysis and drugs of abuse screen
- A blood sample for serology (HIV, HbsAg, Hepatitis C)
- A resting blood pressure and heart rate measurement.
- A serum pregnancy test (for women of child-bearing potential)
- A 3-day dietary assessment (See Section [4.1.1.4](#))

- An electrocardiogram (ECG)

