4.1.1.2 Medical History and Complete Physical Exam

A complete medical and drug history will be recorded for each volunteer at the initial screening visit and reviewed for any additions or omissions on admission to the CRC (Day – 1A). Significant medical conditions that have occurred within the past 2 years, or conditions that are ongoing (i.e., headache, backache, indigestion) are to be recorded in the CRF. The drug history must identify any known drug allergies, presence or history of drug abuse, and use of chronic medications.

The complete physical examination will include an assessment of the following:

- General appearance,
- Skin, head, neck, and lymph nodes
- Musculoskeletal/extremities (including spine)
- Cardiovascular
- Lungs
- Abdomen
- Neurological (reflexes)

Physical examination data to be recorded on the CRF will include: 1) normal/abnormal and 2) a description of any abnormalities.

Height in centimeters (cm) and weight in kg will be measured at screening only and will be recorded on the CRF.

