4.4.1.4 Serum pregnancy test

Female volunteers of childbearing potential will have a serum pregnancy test. The serum pregnancy test can be collected with the same sample as the blood chemistry. If the result is positive, the volunteer will not be allowed to proceed in the trial.

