Absorption: Atorvastatin is rapidly absorbed after oral administration; maximum plasma concentrations occur within 1 to 2 hours. Extent of absorption increases in proportion to atorvastatin dose. The absolute bioavailability of atorvastatin (parent drug) is approximately 14% and the systemic availability of HMG-CoA reductase inhibitory activity is approximately 30%. The low systemic availability is attributed to presystemic clearance in gastrointestinal mucosa and/or hepatic first-pass metabolism. Although food decreases the rate and extent of drug absorption by approximately 25% and 9%, respectively, as assessed by C_{max} and AUC, LDL-C reduction is similar whether atorvastatin is given with or without food. Plasma atorvastatin concentrations are lower (approximately 30% for C_{max} and AUC) following evening drug administration compared with morning. However, LDL-C reduction is the same regardless of the time of day of drug administration (see DOSAGE AND ADMINISTRATION).

Distribution: Mean volume of distribution of atorvastatin is approximately 381 liters. Atorvastatin is ×98% bound to plasma proteins. A blood/plasma ratio of approximately 0.25 indicates poor drug penetration into red blood cells. Based on observations in rats, atorvastatin is likely to be secreted in human milk (see CONTRAINDICATIONS, Pregnancy and Lactation, and PRECAUTIONS, Nursing Mothers).

Metabolism: Atorvastatin is extensively metabolized to ortho- and parahydroxylated derivatives and various beta-oxidation products. *In vitro* inhibition of HMG-CoA reductase by ortho- and parahydroxylated metabolites is equivalent to that of atorvastatin. Approximately 70% of circulating inhibitory activity for HMG-CoA reductase is attributed to active metabolites. *In vitro* studies suggest the importance of atorvastatin metabolism by cytochrome P450 3A4, consistent with increased plasma concentrations of atorvastatin in humans following coadministration with erythromycin, a known inhibitor of this isozyme (see PRECAUTIONS, Drug Interactions). In animals, the ortho-hydroxy metabolite undergoes further glucuronidation.

Excretion: Atorvastatin and its metabolites are eliminated primarily in bile following hepatic and/or extra-hepatic metabolism; however, the drug does not appear to undergo

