Atherosclerosis is a chronic process and discontinuation of lipid-lowering drugs during pregnancy should have little impact on the outcome of long-term therapy of primary hypercholesterolemia. Cholesterol and other products of cholesterol biosynthesis are essential components for fetal development (including synthesis of steroids and cell membranes). Since HMG-CoA reductase inhibitors decrease cholesterol synthesis and possibly the synthesis of other biologically active substances derived from cholesterol, they may cause fetal harm when administered to pregnant women. Therefore, HMG-CoA reductase inhibitors are contraindicated during pregnancy and in nursing mothers.

ATORVASTATIN SHOULD BE ADMINISTERED TO WOMEN OF CHILDBEARING AGE ONLY WHEN SUCH PATIENTS ARE HIGHLY UNLIKELY TO CONCEIVE AND HAVE BEEN INFORMED OF THE POTENTIAL HAZARDS.

If the patient becomes pregnant while taking this drug, therapy should be discontinued and the patient apprised of the potential hazard to the fetus.

WARNINGS

Liver Dysfunction

HMG-CoA reductase inhibitors, like some other lipid-lowering therapies, have been associated with biochemical abnormalities of liver function. **Persistent elevations (>3 times the upper limit of normal [ULN] occurring on 2 or more occasions) in serum transaminases occurred in 0.7% of patients who received atorvastatin in clinical trials. The incidence of these abnormalities was 0.2%, 0.2%, 0.6%, and 2.3% for 10, 20, 40, and 80 mg, respectively.**

One patient in clinical trials developed jaundice. Increases in liver function tests (LFT) in other patients were not associated with jaundice or other clinical signs or symptoms. Upon dose reduction, drug interruption, or discontinuation, transaminase levels returned to or near pretreatment levels without sequelae. Eighteen of 30 patients with persistent LFT elevations continued treatment with a reduced dose of atorvastatin.

It is recommended that liver function tests be performed prior to and at 12 weeks following both the initiation of therapy and any elevation of dose, and periodically (eg, semiannually) thereafter. Liver enzyme changes generally occur in the first 3 months of treatment with atorvastatin. Patients who develop increased transaminase levels should be monitored until the abnormalities resolve. Should an increase in ALT or AST of >3 times ULN persist, reduction of dose or withdrawal of atorvastatin is recommended.

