In a study in rats given 20, 100, or 225 mg/kg/day, from gestation day 7 through to lactation day 21 (weaning), there was decreased pup survival at birth, neonate, weaning, and maturity in pups of mothers dosed with 225 mg/kg/day. Body weight was decreased on days 4 and 21 in pups of mothers dosed at 100 mg/kg/day; pup body weight was decreased at birth and at days 4, 21, and 91 at 225 mg/kg/day. Pup development was delayed (rotorod performance at 100 mg/kg/day and acoustic startle at 225 mg/kg/day; pinnae detachment and eye opening at 225 mg/kg/day). These doses correspond to 6 times (100 mg/kg) and 22 times (225 mg/kg) the human AUC at 80 mg/day. Rare reports of congenital anomalies have been received following intrauterine exposure to HMG-CoA reductase inhibitors. There has been one report of severe congenital bony deformity, tracheo-esophageal fistula, and anal atresia (VATER association) in a baby born to a woman who took lovastatin with dextroamphetamine sulfate during the first trimester of pregnancy. LIPITOR should be administered to women of child-bearing potential only when such patients are highly unlikely to conceive and have been informed of the potential hazards. If the woman becomes pregnant while taking LIPITOR, it should be discontinued and the patient advised again as to the potential hazards to the fetus.

Nursing Mothers

Nursing rat pups had plasma and liver drug levels of 50% and 40%, respectively, of that in their mother's milk. Because of the potential for adverse reactions in nursing infants, women taking LIPITOR should not breast-feed (see CONTRAINDICATIONS).

Pediatric Use

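### Inclusion criterion 4 offers not being pregnant or lactating as an alternative to sterilisation or menopause, so a sterilised breast-feeding woman satisfies it as written

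*Protocol*

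**What the plan says.** Protocol 3.3.2, item 4, admits "Women who are surgically sterilized, post-menopausal for at least one year, or not pregnant and/or lactating". Its next sentence deals with contraception for women of childbearing potential (abstinence, double barrier or intrauterine device). Item 2 sets the age range at 18 to 65. In the protocol body, item 4 is the only place that mentions lactation.

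The provisions that bear on it are these:

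- **Exclusion 4 (3.3.3)** bars "Any contraindication determined by review of a detailed medical and drug history, complete physical examination", together with vital signs, blood chemistry, haematology and ECG.
- **4.1.1.2** calls for a complete medical and drug history, with the drug-history content stated as "The drug history must identify any known drug allergies, presence or history of drug abuse, and use of chronic medications". The medical history covers significant conditions of the past 2 years and ongoing conditions. Breast-feeding is not listed.
- **4.4.1.4** has a serum test for women of childbearing potential, with a stop rule for pregnancy: "If the result is positive, the volunteer will not be allowed to proceed in the trial".
- **Appendix D** (atorvastatin label) states for the class that "HMG-CoA reductase inhibitors are contraindicated during pregnancy and in nursing mothers". It also says: "Based on observations in rats, atorvastatin is likely to be secreted in human milk", and "Because of the potential for adverse reactions in nursing infants, women taking LIPITOR should not breast-feed".
- **Appendix E** (simvastatin label) likewise contraindicates the drug in nursing mothers. It says excretion of simvastatin in human milk is unknown, but that a small amount of another drug in the class is excreted.

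**The concern.** Pregnancy and lactation status should be a condition on every woman. Sterilisation, menopause and contraception answer a different question: whether she might conceive during the study. Item 4 puts both on one list and joins them with *or*, so meeting the childbearing condition removes the need to meet the lactation condition.

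The woman this lets through is plausible: someone sterilised around her last delivery who is still nursing. She would receive single doses of three statins, and the labels appended to the protocol contraindicate two of them by name and the class as a whole while nursing. Section 3.2.2 rests its risk assessment on use in line with prescribing information and states that volunteers gain no health benefit, so there is nothing to set against an avoidable infant exposure.

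**Working it through.** There is no figure in the plan to reproduce. The check treats item 4 as a logical condition and then looks for another place where lactation would be caught.

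**1. Item 4 as a condition.** Let S = surgically sterilised, M = post-menopausal for at least a year, P = pregnant, L = lactating. Give the third limb its most favourable reading, neither pregnant nor lactating:

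- As written: S or M or (not P and not L)
- As proposed: (not P and not L) and (S or M or contraception as already listed)

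For a breast-feeding woman who is not pregnant, P is false and L is true, so (not P and not L) is false.

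| S | M | As written | As proposed |
|---|---|---|---|
| yes | yes | met | not met |
| yes | no | met | not met |
| no | yes | met | not met |
| no | no | not met | not met |

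The written criterion is met in 3 of 4 combinations and the proposed wording in 0 of 4. The two post-menopausal rows matter little in practice. The case that counts is the second row, sterilised and not post-menopausal.

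**2. Where else lactation could be caught.** Items naming lactation, nursing or breast-feeding:

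- Exclusion criteria, 3.3.3: 0 of 14
- Restrictions, 3.3.4: 0 of 4
- Screening items, 4.1.1: 0 of 8
- History and examination content listed in 4.1.1.2: none

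Table 1 schedules an inclusion/exclusion check at screening and on Days -1A, -1B and -1C. That check applies item 4 itself, which a sterilised woman already meets.

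**3. Exclusion 4.** Nursing is a contraindication in both appended labels, so exclusion 4 applies to a nursing woman. It operates on what the listed reviews reveal. Blood chemistry, haematology, vital signs and ECG are not designed to identify breast-feeding. The history could, but nothing in it is specified to do so.

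**4. Comparison with pregnancy.** Women of childbearing potential have a named serum test at screening, Day -1A, Day -1B, Day -1C and the Day 4C discharge assessment (Day 3C after simvastatin). That is 5 time points, matching the 5 samples in Table 5, with a stop rule in 4.4.1.4. The test is not given to sterilised women and would not detect lactation in anyone.

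**The case against.** The best answer is that eligibility means the inclusion and exclusion criteria together. Exclusion 4 bars any contraindication, the appended labels make nursing one, and a nursing woman identified at screening is therefore ineligible under the protocol as it stands. Exclusion 5 and the investigator's power to discontinue add discretion. **This stands.** Meeting item 4 does not by itself make her eligible. Its limit is that exclusion 4 depends on nursing coming to light, and exclusion 5 concerns the volunteer's safety and participation, whereas the labelled hazard is to the infant.

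Second, the intent is obvious and most investigators would apply it. Read strictly, item 4 would also shut out men, contrary to item 2, so it only works when read for intent. **This stands too**, and it is a reason to rate the point low. It does not make the wording correct.

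Third, protocols do not usually list every history question. Breast-feeding is known to the volunteer and needs no laboratory test, and three in-patient stays make it harder to overlook. **Largely accepted.** The listed history items are minimum content, the CRF and consent form are not shown, and nothing is claimed about what they ask. The missing question alone would only be missing detail. What remains is the faulty logic of the stated criterion.

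Fourth, the rosuvastatin brochure is not shown. For that drug the contraindication rests on the class sentence in Appendix D.

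**Conclusion.** The point holds, as a minor one. Item 4 is wrong as written: a sterilised breast-feeding woman satisfies it even on the reading most favourable to the sponsor, against the criterion's own intent and the nursing contraindications in Appendices D and E. Exclusion 4 is a real backstop, but an untargeted one.

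The case is expected to be rare. The documents give no basis for a count, and no infant-exposure figure is claimed. Sample size, the evaluable set and the analysis are unaffected. The conclusion rests on the criterion's text and on the absence of lactation from the other eligibility, screening and history provisions. It does not depend on what the CRF or consent form contains.

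**What to change.** Split item 4 into two requirements:

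1. Every female volunteer must be not pregnant and not lactating.
2. Separately, she must be surgically sterilised, or at least one year post-menopausal, or abstaining or using one of the contraceptive methods already listed in item 4.

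Add one question on breast-feeding to the screening history in 4.1.1.2.

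The cost is rewording one criterion and adding one history question. No visit, procedure or blood sample is added, and the design and analysis do not change.

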3.3.3 Exclusion criteria

Any of the following is regarded as a criterion for exclusion from the study:

1. Use of prescription medication for a chronic medical condition
2. Acute illness or use of prescription medication for an acute medical condition within 2 weeks of Day -1A
3. History within the last 3 months of extreme or therapeutic diet programs including but not limited to: weight reduction, weight augmentation, high protein, high carbohydrate, low carbohydrate, or low fat
4. Any contraindication determined by review of a detailed medical and drug history, complete physical examination, vital signs, blood chemistry, hematology, and electrocardiogram (ECG).
5. Medical history or psychological conditions which, in the opinion of the investigator, would compromise the volunteer's safety or successful participation in the study
6. History of severe allergies
7. History of adverse drug reaction or hypersensitivity to statins or drugs with a similar chemical structure.
8. History or presence of gastrointestinal, hepatic, or renal disease or other conditions known to interfere with the ADME of drugs
9. History of alcohol or substance abuse within the past year
10. Positive test results for human immunodeficiency virus (HIV) antibody, hepatitis B surface antigen (HBsAG), or hepatitis C antibody
11. Positive urine drug screen
12. Participation in another study within 30 days of Day -1A, apart from non-invasive methodology studies in which no drugs were given.

13. Involvement in the planning and conduct of the study (applies to both AstraZeneca staff or staff at the study site)
14. Blood donation within 3 months of Day -1A.

3.3.4 Restrictions

Volunteers will be required to:

1. Refrain from alcohol, grapefruit containing products, and apple juice from CRC admission through completion of the study including the washout periods.
2. Refrain from using over-the-counter (OTC) medications, and herbal supplements 1 week prior to CRC admission through the final study assessments including the washout periods. (See Section 3.4.4)
3. Refrain from strenuous exercise during the screening period, washout periods and through final study assessments and discharge from the study.
4. Refrain from eating or drinking starting 10 hours before study drug administration and continuing through 4 hours post study drug administration (with the exception of water which will be allowed ad libitum until 2 hours prior to study drug administration and 2 hours post study drug administration). Lunch will be served approximately 4 hours after dosing. At all other times during the in-patient periods, volunteers will be served standard meals on a regular basis.

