- summarize and compare the plasma exposure of rosuvastatin, atorvastatin, and simvastatin after a single dose in healthy Chinese and Japanese volunteers to the plasma exposure of Caucasian volunteers following a single dose by measuring maximum concentration (C_{max}) and area under the concentration curve from zero to infinity (AUC).

The secondary objectives of this study are to:

- summarize the pharmacokinetics of rosuvastatin, atorvastatin, and simvastatin and the relevant metabolites of each by calculating area under the curve of plasma concentration against time from zero to time of last quantifiable concentration ($AUC_{(0-t)}$), terminal elimination half-life ($t_{1/2\lambda_z}$), time of maximum concentration (t_{max}), terminal elimination rate constant (λ_z) and, (for parent compound only), apparent oral clearance (CL/F).
- calculate parent to metabolite ratios of rosuvastatin metabolites (N-desmethyl rosuvastatin, and rosuvastatin lactone), atorvastatin metabolites (ortho-hydroxy atorvastatin and para-hydroxy atorvastatin) and simvastatin acid.
- obtain deoxyribonucleic acid (DNA) samples.
- assess safety and tolerability

Study design

This is a single center, randomized, open label, 3-way crossover study in healthy Chinese, Japanese, and Caucasian volunteers.

Investigational product, dosage and mode of administration

Rosuvastatin calcium will be administered as a 20 milligram (mg) oral tablet. Atorvastatin calcium will be administered as a 40 mg oral tablet. Simvastatin will be administered as a 40 mg oral tablet.

Duration of treatment

Volunteers meeting inclusion/exclusion criteria and satisfactorily completing screening evaluations during the screening period will participate in a 29-day study that will include 3 in-patient periods (Treatment Periods A, B, C) lasting 4 nights and 5 days with washout periods of at least 7 days between each in-patient period.

Variables

- Pharmacokinetic

C_{max} and AUC of rosuvastatin, atorvastatin, and simvastatin will be the primary endpoints for this study to summarize exposure in the selected populations. A detailed description of the summaries will be described in the Statistical Analyses Plan (SAP).

Along with C_{max} and AUC, $AUC_{(0-t)}$, $t_{1/2\lambda_z}$, t_{max} , λ_z and, (for parent compound only), CL/F of rosuvastatin, atorvastatin, and simvastatin and relevant metabolites will be determined to summarize the pharmacokinetics in the selected populations.

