3. STUDY PLAN AND PROCEDURES

3.1 Overall study design

This is a single-center, open label, randomized, 3-way crossover, pharmacokinetic study comparing plasma exposure in healthy Chinese, Japanese, and Caucasian volunteers after a single dose of rosuvastatin calcium, atorvastatin calcium and simvastatin. Approximately 90 volunteers will be recruited to obtain a minimum of 27 evaluable volunteers per ethnic group.

Volunteers that have met all of the inclusion/exclusion criteria and that have satisfactorily completed the screening evaluations will be randomly assigned, within each ethnic group, to

one of three treatment sequences as determined by a randomization schedule that will be prepared by AstraZeneca.

The study will be completed in 3 Treatment Periods, (A, B, C) each lasting 5 days and 4 nights separated by a washout period of at least 7 days.

Treatment sequences are described as follows:

- Treatment Sequence 1
 - 20 mg rosuvastatin calcium during Treatment Period A
 - 40 mg atorvastatin calcium during Treatment Period B
 - 40 mg simvastatin during Treatment Period C
- Treatment Sequence 2
 - 40 mg atorvastatin calcium during Treatment Period A
 - 40 mg simvastatin during Treatment Period B
 - 20 mg rosuvastatin calcium during Treatment Period C
- Treatment Sequence 3
 - 40 mg simvastatin during Treatment Period A
 - 20 mg rosuvastatin calcium during Treatment Period B
 - 40 mg atorvastatin calcium during Treatment Period C

The study will proceed as follows:

Treatment Period A: Volunteers will come to the clinical research center (CRC) and complete Day –1A assessments as described in the Study Plan ([Table 1](#)).

Prior to dosing on Day 1A, a 10-milliliter (mL) fasting (10 hour) blood sample will be taken for a lipid profile that will include total cholesterol (TC), triglycerides (TG), high density lipoprotein cholesterol (HDL-C), and low density lipoprotein cholesterol (LDL-C).

On Day 1A, volunteers will receive a single dose of study drug (according to their Treatment Sequence) under fasting conditions. Blood samples for those volunteers taking rosuvastatin calcium and atorvastatin calcium will be taken pre-dose (within 30 minutes) and 0.5, 1, 2, 3, 4, 5, 6, 8, 10, 12, 18, 24, 30, 36, 48, 54, 60, and 72 hours post dose. Blood samples for those volunteers taking simvastatin will be taken pre-dose (within 30 minutes) and 0.5, 1, 2, 3, 4, 5, 6, 8, 10, 12, 18, 24, 30, 36, and 48, hours post-dose. Volunteers will be discharged after

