3.4.2 Doses and treatment regimens

On the morning of Day 1 of each Treatment Period (A, B, C) all volunteers will receive a single dose of rosuvastatin calcium, atorvastatin calcium or simvastatin according to their assigned Treatment Sequence under fasting conditions. (See Restrictions Section 3.3.4). Tablets will be taken orally with 240 mLs of distilled, room temperature water. Tablets are not to be crushed or chewed. Volunteers must remain in an upright position (sitting or standing) for 4 hours after dosing.

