Simvastatin is a substrate for CYP3A4 (see PRECAUTIONS, *Drug Interactions*). Grapefruit juice contains one or more components that inhibit CYP3A4 and can increase the plasma concentrations of drugs metabolized by CYP3A4. In one study², 10 subjects consumed 200 mL of double-strength grapefruit juice (one can of frozen concentrate diluted with one rather than 3 cans of water) three times daily for 2 days and an additional 200 mL double-strength grapefruit juice together with, and 30 and 90 minutes following, a single dose of 60 mg simvastatin on the third day. This regimen of grapefruit juice resulted in mean increases in the concentration (as measured by the area under the concentration-time curve) of active and total HMG-CoA reductase inhibitory activity [measured using a radioenzyme inhibition assay both before (for active inhibitors) and after (for total inhibitors) base hydrolysis] of 2.4-fold and 3.6-fold, respectively, and of simvastatin and its η -hydroxyacid metabolite [measured using a chemical assay — liquid chromatography/tandem mass spectrometry] of 16-fold and 7-fold, respectively. In a second study, 16 subjects consumed one 8 oz glass of single-strength grapefruit juice (one can of frozen concentrate diluted with 3 cans of water) with breakfast for 3 consecutive days and a single dose of 20 mg simvastatin in the evening of the third day. This regimen of grapefruit juice resulted in a mean increase in the plasma concentration (as measured by the area under the concentration-time curve) of active and total HMG-CoA reductase inhibitory activity [using a validated enzyme inhibition assay different from that used in the first² study, both before (for active inhibitors) and after (for total inhibitors) base hydrolysis] of 1.13-fold and 1.18-fold, respectively, and of simvastatin and its η -hydroxyacid metabolite [measured using a chemical assay — liquid chromatography/tandem mass spectrometry] of

² Lilja JJ, Kivisto KT, Neuvonen PJ. Clin Pharmacol Ther 1998;64(5):477-83.

1.88-fold and 1.31-fold, respectively. The effect of amounts of grapefruit juice between those used in these two studies on simvastatin pharmacokinetics has not been studied.

Clinical Studies in Adults

Reductions in Risk of CHD Mortality and Cardiovascular Events

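### The grapefruit restriction starts only at first admission, one night before the Period A dose, leaving simvastatin (and possibly atorvastatin) in Period A open to a residual effect that Periods B and C are protected from

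*Protocol*

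**What the plan says.** Section 3.3.4, item 1, tells volunteers to "Refrain from alcohol, grapefruit containing products, and apple juice from CRC admission through completion of the study including the washout periods". Item 2 of the same list has an earlier start: "Refrain from using over-the-counter (OTC) medications, and herbal supplements 1 week prior to CRC admission through the final study assessments including the washout periods". Section 3.4.4 repeats that 1-week lead for over-the-counter, dietary and herbal products. It also counts the week before CRC entry as part of the restricted time for prescription drugs.

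The schedule fixes the timing. In section 3.1 the first arrival is Day -1A ("Volunteers will come to the clinical research center (CRC) and complete Day" -1A assessments). The synopsis describes in-patient periods "lasting 4 nights and 5 days with washout periods of at least 7 days between each in-patient period". Section 3.4.2 sets the dose time: "On the morning of Day 1 of each Treatment Period (A, B, C) all volunteers will receive a single dose". Besides the admission rule, the only barrier before the Period A dose is the 10-hour fast in section 3.3.4, item 4. No exclusion criterion mentions juice.

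The simvastatin label in Appendix E says that grapefruit juice inhibits CYP3A4 and that simvastatin is a CYP3A4 substrate. In one of its two studies, 16 subjects took one single-strength glass "with breakfast for 3 consecutive days and a single dose of 20 mg simvastatin in the evening of the third day". AUC of simvastatin and of its acid, measured by chemical assay, rose "1.88-fold and 1.31-fold, respectively".

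**The concern.** Restriction 1 runs through both washouts, so Periods B and C are well covered. Period A is not. Sequence 3 receives simvastatin in Period A, so part of the simvastatin data is exposed to juice drunk up to admission. Sequence 2 receives atorvastatin in Period A, and the atorvastatin label (Appendix D, Metabolism) also points to CYP3A4, so the same may apply there.

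The analysis does not cancel such an effect. The model in section 6.4.4 has a period term common to the three drugs, and an effect confined to one drug in one period is not a common period effect. The primary question in section 6.4.2 is a ratio of ethnic ratios with rosuvastatin in the denominator. Section 1.1.1 says that rosuvastatin clearance does not depend on CYP3A4 to a clinically significant extent, so the denominator would not move in step. Randomization to sequence within ethnic group does not balance juice habits between ethnic groups. If habits differ, the simvastatin contrast is biased. If they do not, some noise is still added.

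**Working it through.** **Timeline.** The 29-day study in the synopsis is 5 + 7 + 5 + 7 + 5. With Day -1A as study day 1:

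| Period | Dose on study day | Restricted days before the dose |
|---|---|---|
| A | 2 | about 1 (never less than the 10-hour fast) |
| B | 14 | about 13 |
| C | 26 | about 25 |

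**The plan's own figure, as background.** Section 6.4.5 gives 27 per group for AUC with limits 0.7 to 1.43, expected ratio 1 and 90% power. It states no SD, so 27 can only be solved backwards. I used two one-sided 5% tests (matching the 90% CI in section 6.4.4) on the between-group difference of within-subject log-AUC differences:

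- margin m = ln(1/0.7) = 0.357; SE = sd_D × √(2/27); t = 1.675 on 52 df
- power = Φ((m − θ)/SE − t) + Φ((m + θ)/SE − t) − 1
- 90% power at θ = 0 gives sd_D = 0.395, SE = 0.107, variance 0.395² = 0.156

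**Assumptions for the illustration (none is in the documents).**

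- One third of each ethnic group receives simvastatin in Period A.
- The effect in juice users lies between 1.88-fold (label effect in full, ln 1.88 = 0.631) and 1.37-fold (half the log effect, 0.316). The lower value is a chosen discount for a longer gap, not a documented bound.
- Use differs by 20 percentage points between two ethnic groups.

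**Shift of the simvastatin ratio of ratios**, exp(difference in use × log effect / 3):

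- full effect: exp(0.2 × 0.631/3) = exp(0.042) = 1.043; power 87.4%
- half effect: exp(0.2 × 0.316/3) = exp(0.021) = 1.021; power 89.3%

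At the full 1.88-fold effect, a 10-point difference gives 1.021 (89.3%) and a 30-point difference gives 1.065 (84.2%).

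**Added variance with 20% users and no ethnic difference.** Within Sequence 3, p(1 − p) × (log effect)² is 0.16 × 0.398 = 0.064 at full effect and 0.16 × 0.0996 = 0.016 at half. Only one sequence in three is affected, so the average added to the variance of the simvastatin-minus-rosuvastatin difference is 0.064/3 = 0.021, or 0.016/3 = 0.0053. Against 0.156 that is about 14%, or 3%.

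**The case against.** Different start points for different exposures can be a deliberate choice, and nothing in the protocol says that a week without juice is needed. That stands: this is an asymmetry that can be avoided cheaply, not a contradiction that invalidates the design.

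The label study also does not match this trial's gap. There the drug followed breakfast juice the same evening, after 3 days of daily use. Here the last permitted juice comes before admission on the previous day, with at least a 10-hour fast. The label shows that an effect can survive hours of separation, but not how much remains here. The same study found only 1.13- and 1.18-fold for active and total inhibitory activity. The trial's endpoint is simvastatin itself by LC/MS/MS (section 4.2.1), so 1.88 is the matching figure, but it is not an estimate for this gap.

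Nothing in the documents suggests that juice use differs by ethnic group. The 3-day diary in section 4.1.1.4 captures all liquids, so habitual use could be described by group. It need not fall just before Day -1A and restricts nothing.

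Three stronger readings are tempting and are not supported:

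- A reader might take Period A simvastatin alone and infer a bias about three times larger, or set its extra variance against that of a single observation. No Period A-only contrast is planned.
- A reader might use the label's 16-fold figure. That juice was double strength, taken three times daily, and also taken with and after the dose, which the fast precludes.
- A reader might extend the point to apple juice because it is in the same item. No passage reports an apple-juice effect on simvastatin.

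**Conclusion.** The point holds as a modest design weakness. That Period A has about one restricted day against at least 7 for the other periods follows directly from the protocol. That simvastatin responds to grapefruit juice taken hours earlier follows from its own appendix. Atorvastatin in Period A may share the exposure, but the documents give no grapefruit effect size for it.

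The size is unknown. Under the stated assumptions the planned contrast moves by about 2% to 4%, power falls from 90% to about 87% to 89%, and the variance of the within-subject difference rises by about 3% to 14%. These figures rest on assumed juice use, an assumed ethnic difference, an assumed residual effect and an SD back-solved from n = 27. They do not show that the primary comparison is compromised.

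**What to change.** Reconcile the start of the grapefruit restriction in section 3.3.4, item 1, with the window opening 1 week before admission that item 2 and section 3.4.4 already use, so that all three periods follow a comparable grapefruit-free interval. If the later start is intended, state the reason in view of the Appendix E data. Record any lapse at Day -1A.

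The cost is one line in section 3.3.4 and in the screening instructions. Volunteers are already seen in the 35-day screening period, so no visit is added. The downside is slightly more burden on volunteers before admission. Priority is low.
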